### MEMORANDUM

**TO:** [name]

**FROM:** [name]  
Chair, Institutional Review Board for the Protection of Human Subjects

**DATE:** April 20, 2020

**SUBJECT:** *"Nen Onk?umbi/Edahiyedo ("We Are Here Now"? - a Multi-level, Multi-component Sexual and Reproductive Health Intervention for American Indian Youth- Pilot Study" [ER020518]*

This is to acknowledge receipt of the request dated April 20, 2020 for minor modifications to the above protocol. The request for the following modifications is approved:

- Protocol is being changed for parents to read and complete a parent educational packet of resources alongside one-on-one meetings with our Native implementors, rather than group educational sessions;
- Request to include Focus Groups focused on Fidelity, Acceptability, and Sustainability of the project implementation to be conducted in summer 2020. A total of 8 focus groups will be conducted including two focus groups with youth participants, two focus groups with parents of youth participants, 2 focus groups surrounding the cultural mentoring components of the intervention, and 2 focus groups with professionals involved in the intervention.

### MEMORANDUM

**TO:** [name], [name], [name], [name]

**FROM:** [name]  
Chair, Institutional Review Board for the Protection of Human Subjects

**DATE:** September 30, 2020

**SUBJECT:** *"Nen Onk?umbi/Edahiyedo ("We Are Here Now') - a Multi-level, Multi-component sexual and Reproductive Health Intervention for American Indian Youth [ER100318-FCJ*

This is to acknowledge receipt of the request dated September 29, 2020 for minor modifications to the above protocol. The request for the following modifications is approved:

- Will conduct a within scope data collection of the impact of COVID-19 on their primary outcome variables and the study's stepped wedge design.
- Will be collecting data from a subset of the study participants. The data collection will include: a chain referral network survey and in-depth interviews.
- Submitted the consent forms and data collection instruments for the two methods of data collection.

# **ClinicalTrials.gov PRS**

## **Protocol Registration and Results System**

---

ClinicalTrials.gov Protocol Registration and Results System (PRS) Receipt  
Release Date: October 1, 2018

ClinicalTrials.gov ID: NCT03694418

---

### **Study Identification**

Unique Protocol ID: R01MD012761

Brief Title: We Are Here Now: a Multi-level, Multicomponent Sexual and Reproductive Health Intervention for American Indian Youth ( NE)

Official Title: We Are Here Now: a Multi-level, Multicomponent Sexual and Reproductive Health Intervention for American Indian Youth

Secondary IDs:

### **Study Status**

Record Verification: October 2018

Overall Status: Not yet recruiting

Study Start: March 1, 2019 [Anticipated]

Primary Completion: November 30, 2021 [Anticipated]

Study Completion: November 30, 2022 [Anticipated]

## Study Description

**Brief Summary:** N/E is a community-based participatory research (CBPR) multi-level, multi-component sexual and reproductive health (SRH) intervention, constructed on Ecological Systems Theory. N/E is based on Fort Peck tribal members' desire to implement a holistic SRH intervention for AI youth. N/E includes: 1) A school-based SRH curriculum called Native Stand, designed to address individual-level factors that lead to sexual risk behaviors; 2) a family-level curriculum called Native Voices, tailored to increase communication between adult family members and youth about SRH topics; 3) a cultural mentoring component at the community level that pairs AI youth with adults and elders to discuss traditional AI beliefs and practices about SRH; and 4) a mobilizing strategy to activate a multi-sectoral network of youth-servicing organizations at the systems level in Fort Peck to coordinate SRH services for AI youth. The overarching aim of this proposal is to refine, tailor, and finalize the components of N/E and evaluate its efficacy. We will use a cluster-randomized stepped-wedge design (SWD), in which 5 schools that AI youth from Fort Peck attend are the clusters to be randomized into the intervention 1 at a time, with all schools eventually being randomized to the intervention. The 5 schools are located in separate communities, mitigating the potential for cross-contamination. N/E is a 5-year study involving 456 15- to 18-year-old AI youth.

**Detailed Description:** N/E is a community-based participatory research (CBPR) multi-level, multi-component sexual and reproductive health (SRH) intervention, constructed on Ecological Systems Theory. N/E is based on Fort Peck tribal members' desire to implement a holistic SRH intervention for AI youth. N/E includes: 1) A school-based SRH curriculum called Native Stand, designed to address individual-level factors that lead to sexual risk behaviors; 2) a family-level curriculum called Native Voices, tailored to increase communication between adult family members and youth about SRH topics; 3) a cultural mentoring component at the community level that pairs AI youth with adults and elders to discuss traditional AI beliefs and practices about SRH; and 4) a mobilizing strategy to activate a multi-sectoral network of youth-servicing organizations at the systems level in Fort Peck to coordinate SRH services for AI youth. The overarching aim of this proposal is to refine, tailor, and finalize the components of N/E and evaluate its efficacy. We will use a cluster-randomized stepped-wedge design (SWD), in which 5 schools that AI youth from Fort Peck attend are the clusters to be randomized into the intervention 1 at a time, with all schools eventually being randomized to the intervention. The 5 schools are located in separate communities, mitigating the potential for cross-contamination. N/E is a 5-year study involving 456 15- to 18-year-old AI youth.

Our specific aims are:

**AIM 1:** Refine, tailor, and finalize the components of N/E. Our community advisory board and the Fort Peck-based and MSU-based research team will design culturally appropriate adaptations for N/E's 4 levels during the first year of the study, based on the analysis of our recently completed qualitative and quantitative research (focus groups, interviews, and surveys), as well as discussions with elders and community stakeholders.

**AIM 2:** Test the efficacy of N/E for 15- to 18-year-old AI youth. Our hypotheses are:

H1: AI youth who participate in N/E will demonstrate increased condom use at 3, 9, and 12 months. (12 months will be used in the Primary Outcome analysis; 3 and 9 months will be used in the Secondary Outcomes analysis.) H2: AI youth who participate in N/E will demonstrate increased use of other birth control at 3, 9, and 12 months. They also will demonstrate a decrease in sexual risk behaviors as measured by reduced number of sex partners, delayed onset of sexual intercourse, and decreased substance use during sex, at 3, 9, and 12 months. (Secondary Outcomes) H3: N/E parents/legal guardians and youth will demonstrate significantly increased communication about topics related to SRH at 3, 9, and 12 months. AI youth who participate in the cultural mentoring program will demonstrate significantly increased understanding of cultural values related to traditional AI beliefs regarding SRH at 3, 9, and 12 months. And AI youth who participate in N/E will report significantly increased use of SRH services at 3, 9, and 12 months as a result of improved coordination among education, health care, and social service agencies on the Fort Peck Reservation. (Tertiary Outcomes) AIM 3: Evaluate the fidelity and acceptability of N/E. N/E's fidelity and acceptability will be evaluated using qualitative methods, including focus groups, activity logs, and staff field notes and meetings.

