**Table 1. Overview of *NIE*'s 9-month multi-level, multi-component intervention plan.**

INDIVIDUAL	FAMILY	COMMUNITY	SYSTEMS
Native Stand (NS): 18-session school-based curriculum delivered twice a month over 9 months in NIE 's 5 participating schools. NS will be integrated into the schools' existing class schedules.	Native Voices (NV): 4 sessions delivered once every other month to students and parents/legal guardians after school hours at NIE 's 5 participating schools.	Cultural Mentoring Program (CMP): 9 mentoring sessions delivered twice a month over 9 months that include one group activity with CMP mentors and mentees and one 1:1 meeting. CMP activities will take place at varying locations on the Reservation depending on the activity.	SRH Services: Monthly meetings over 12 months with Epi Team at the Fort Peck Tribes Headquarters offices in Poplar, Montana.
NS 1: Introduction to an overview of NIE and Native Stand	NV 1: Introduction to an overview of NIE and Native Voices	CMP 1: Assiniboine/Sioux kinship networks and concepts of family and genealogy	Epi Team meetings will take place monthly over 9 months to enhance coordination and implementation of SRH services for AI youth.
NS 2: Culture & Tradition – Part 1		CMP 2: Traditional male/female roles and cultural beliefs about healthy relationships	
NS 3: Culture & Tradition – Part 2		CMP 3: Cultural beliefs about sex and how to make decisions about sex that integrate cultural values	
NS 4: Healthy Relationships – Part 1		CMP 4: Cultural beliefs about parenting and the role of family	
NS 5: Healthy Relationships – Part 2		CMP 5: The role of ceremony in traditional Assiniboine/Sioux culture	
NS 6: Reproductive Health – Part 1		CMP 6: The role of sweat lodges in AI spirituality	
NS 7: Reproductive Health – Part 2		CMP 7: Honoring ceremonies in the lives of young men and women	
NS 8: Pregnancy & Parenting		CMP 8: Understanding the sacredness of the land	
NS 9: Preventing Pregnancy		CMP 9: Buffalo Harvest	
NS 10: Condoms & Birth Control			
NS 11: Sexually Transmitted Diseases			
NS 12: HIV/AIDS & HCV			
NS 13: Drugs, Alcohol, & Sex	NV 3: Prevention of STIs, HIV/AIDS, and HCV		
NS 14: Mental Health & Sex			
NS 15: Negotiation & Refusal Skills			
NS 16: Decision-Making			
NS 17: Effective Communication			
NS 18: Putting It All Together			

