### SECTION 3: ANALYSIS PLAN

**3.1.1 Power analysis.** Sample size requirements were calculated taking into account a unique design effect for the SWD, such that  $N_{sw} = Nu \times DE_{sw}$  (where  $Nu$  is the total number of students needed to detect the treatment effect with a power of 80% and a significance level of 0.05, uncorrected for cluster and repeated measurements). The design effect was calculated as:

$$DE_{sw} = \frac{1 + \rho(ktn + bn - 1)}{1 + \rho\left(\frac{1}{2}ktn + bn - 1\right)} \times \frac{3(1 - \rho)}{2t(k - \frac{1}{k})}$$

where  $k$  is the number of steps,  $n$  is the expected number of students per cluster,  $b$  is the number of baseline measurements,  $t$  is the number of measurements after each step, and  $\rho$  is the intra-class correlation coefficient, estimated to be 0.016 based on findings reported by Kaufman et al. With an  $\rho$  of 0.05, power of 0.8,  $Nu = 292$ ,  $DE_{sw} = 1.3273$ , and the expectation of 15% attrition during the study, a sample size of 456 will allow the detection of a 0.14 increase in the proportion of condom use relative to the frequency of sexual intercourse from baseline to the 12-month observation period hypothesized under Aim 2.

**3.1.2 Missing data.** Attrition is likely to covary with truancy, suggesting a missing data mechanism that is not missing at random (NMAR). To address this, a dropout variable  $D_i$  will be developed for each individual across the 4 observation periods, where  $D_i=k$  for dropout between the  $(k-1)$  and  $k^{\text{th}}$  occasion. A model of the probability of dropout, where

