From Years 2-4, 456 students and one of their parents/legal guardians will participate in *NIE*'s data collection. Student surveys for baseline, 3, and 9 months will be administered during regularly scheduled classes in an assigned classroom by [name], the assistant, and N/E's outreach coordinator. Baseline data collection will begin in March 2019 for all schools and parents included in the intervention. Groups of 20 students at a time will be appropriately spaced in the classroom in order to ensure privacy, and survey instructions will be presented to students prior to REDCap administration. [name], the assistant, and the *NIE* outreach coordinator will thoroughly review the assent form with the students, which will include a description of *NIE*, types of questions that will be asked, and potential risks and benefits of participating in *NIE*. All students will be reminded that they can withdraw at any time without consequences. Prior similar procedures have been successfully used by [name] and [name] for data collection in the Fort Peck schools with AI youth. For students who graduate from high school prior to the 12-month follow-up, they and their parent/legal guardian will be contacted by [name] to complete the 12-month follow-up (during evening hours) at the high school from which they graduated following the same procedure described above. Although data collection for the students has been designed to coincide with the school year, the same procedures will be followed if the data collection occurs when school is not in session.

Wave 1 data collection will commence in December 2019 with 1 school after students have begun receiving the Native Stand and Cultural Mentoring components of the intervention during the school year.

Wave 1 9- month follow-up will take place at the end of the school year in May/June 2020 as the intervention is completed. The Wave 1 12-month follow-up will take place at the beginning of the next school year in September 2020.

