## Outcome Measures

### Primary Outcome Measure:

1. Change in condom use during sexual intercourse at 3 months, 9 months and 12 months

Change in condom use during sexual intercourse will be measured as proportion of condom use during sexual intercourse will be measured using 2 items (number of times condom used relative to number of times had sexual intercourse).

[Time Frame: 3 months, 9 months and 12 months]

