5.3 During your life, with how many people have you had sexual intercourse?

- a. 1 person
- b. 2 people
- c. 3 people
- d. 4 people
- e. 5 people
- f. 6 or more people

5.4 During the past month, how many people have you had sex with? \_\_\_\_\_ [# of people]

5.5 During the past month, how many TIMES have you had sex? \_\_\_\_\_ times

5.6 Of the times you had sex over the past month, how many TIMES was a condom used?  
\_\_\_\_\_ times

5.7 Of the times you had sex over the past month, how many TIMES did you use birth control other than a condom, like birth control pills or having a deprova shot?  
\_\_\_\_\_ times

Over the past month, did you drink alcohol or take any kind of drug and have sex? Yes No

5.9 Did you drink alcohol or use drugs before you had sexual intercourse the **last** time?

- a. I have never had sexual intercourse
- b. Yes
- c. No

5.10 The last time you had sexual intercourse, what one method did you or the person you had sex with use to prevent pregnancy? (Select only one response.)

- a. No method was used to prevent pregnancy
- b. Birth control pills
- c. Condoms
- d. An IUD (such as Mirena or ParaGard) or implant (such as Implanon or Nexplanon)
- e. A shot (such as Depo-Provera), patch (such as OrthoEvra), or birth control ring (such as NuvaRing)
- f. Withdrawal or some other method
- g. Not sure

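### The 3-month survey measures partial exposure, and the Aim 2 model does not keep it apart from the 12-month effect that is meant to be primary

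*Combined protocol and SAP*

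**What the plan says.** - **Hypotheses.** In the ClinicalTrials.gov record (Detailed Description, Aim 2), H1 reads "AI youth who participate in N/E will demonstrate increased condom use at 3, 9, and 12 months". A parenthesis directly after it assigns 12 months to the primary analysis and 3 and 9 months to the secondary analyses. The year-one progress report repeats this. H2 covers other birth control, partners, onset of intercourse and substance use during sex at the same three times.
- **Registered primary outcome.** The outcome list of the same record gives "Change in condom use during sexual intercourse at 3 months, 9 months and 12 months" and does not single out 12 months.
- **Delivery.** Table 1 describes Native Stand as an "18-session school-based curriculum delivered twice a month over 9 months". The tenth session is "NS 10: Condoms & Birth Control".
- **Survey date.** The progress report (item B.6) starts the first school in September 2019. Section 4.1 says "Wave 1 data collection will commence in December 2019 with 1 school after students have begun receiving the Native Stand and Cultural Mentoring components".
- **Measure.** Student survey item 5.6 asks "Of the times you had sex over the past month, how many TIMES was a condom used".
- **Model.** The mixed-model section (the second of the two numbered 3.1.5) has period effects, a school random effect and a single intervention effect, theta. The exposure variable X is 0/1 or a dose. Section 3.1.3 bases dose on components delivered to the student and leaves its form until the dose distribution has been seen.
- **Power.** Section 3.1.1 says "a sample size of 456 will allow the detection of a 0.14 increase in the proportion of condom use", from baseline to 12 months.

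**The concern.** H1 and H2 predict a change in condom use, birth control and substance use with sex at a survey that precedes the Native Stand sessions on those subjects. The one-month recall of the condom item moves the measured behaviour earlier still. At that survey the student's school has already crossed over. Under 0/1 coding its 3-month rows therefore enter theta with the same weight of exposure as rows collected after the full programme.

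The record names 12 months as primary, but the model contains nothing that produces a 12-month estimate. An analyst following Section 3.1.5 as written could report one theta that mixes partial and full exposure, and the registered outcome list would support that choice. The estimate would then understate the effect of the completed programme if the effect grows with exposure.

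**Working it through.** **1. The plan's own figure.** Inputs from Section 3.1.1: Nu = 292, design effect 1.3273, attrition 15%.

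292 x 1.3273 = 387.57, and 387.57 / 0.85 = 455.97, so 456. The total reproduces. It is stated for a change at 12 months.

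**2. What has been delivered at 3 months.** Month of delivery = session number / 2, assuming numbered order and an even pace.

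| Session | Month |
|---|---|
| NS 6 (reproductive health, first part) | 3.0 |
| NS 9 (pregnancy prevention) | 4.5 |
| NS 10 (condoms and birth control) | 5.0 |
| NS 11 (STIs) | 5.5 |
| NS 12 (HIV and HCV) | 6.0 |
| NS 13 (substances and sex) | 6.5 |
| NS 15 (negotiation and refusal) | 7.5 |

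By month 3, 2 x 3 = 6 of 18 sessions are due. A survey at the end of December (month 4, 8 sessions) still precedes NS 9. The recall window reaches back to about month 2.

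Related content that is due by month 3: NS 4-6, and mentoring topics CMP 2 (roles and relationships) and CMP 3 (beliefs and decisions about sex). One or two Native Voices sessions are possible at one every other month. Section 4.1 does not list Native Voices among the components begun by December, and the topic of its second session is not legible in the available text.

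**3. Dilution if the three follow-ups share one 0/1 effect.** Assumptions: equal weights, effect 0.14 at 9 and 12 months, and a share f of it at 3 months.

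Pooled effect = 0.14 x (f + 2)/3.

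For power, take a two-sided 0.05 test (the plan does not state sidedness) whose standard error gives 80% at 0.14. The noncentrality is then 1.96 + 0.84 = 2.80, and power = Phi(2.80 x (f + 2)/3 - 1.96).

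| f | Pooled effect | Noncentrality | Power |
|---|---|---|---|
| 0 | 0.093 | 1.87 | 46% |
| 1/3 | 0.109 | 2.18 | 59% |
| 1/2 | 0.117 | 2.33 | 65% |
| 3/4 | 0.128 | 2.57 | 73% |

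The power column depends on its anchor. Suppose the 80% belongs to a 12-month-only contrast and pooling three surveys shrinks the standard error by sqrt(2/1.333) = 1.225 (the variance model of step 4). Then f = 0 gives 2.80 x 1.225 x 0.667 = 2.29, or 63%, and f = 1/3 gives 2.80 x 1.225 x 0.778 = 2.67, or 76%. The pooled effects do not change.

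**4. Cost of leaving the 3-month rows out.** In a simple model of post-mean minus baseline, the variance is proportional to 1 + 1/3 with three follow-ups and 1 + 1/2 with two. The ratio of standard errors is sqrt(1.5/1.333) = 1.061. Then 2.80/1.061 = 2.64, or about 75% power.

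**5. The same questions in a stepped-wedge layout.** This uses generalised least squares on school-by-period means, with rho 0.016, 91 students per school (456/5), waves of 1, 2 and 2 schools a year apart, and every school surveyed in every period.

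- One 0/1 theta recovers 56% of the full effect if f = 0, and 71% if f = 1/3.
- Dropping each school's 3-month cell raises the standard error by about 14%. Then 2.80/1.14 = 2.46, or about 69% power.

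If each school is surveyed only at baseline and at its own follow-ups, theta cannot be separated from the period effects in this layout, and the figures in this step do not apply.

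**The case against.** **The primary analysis is already protected.** The record says that 12 months is primary, and the 456 is tied to 12 months. A true 12-month contrast takes nothing from the 3-month rows. This stands as far as the stated intention goes. It is not carried into Section 3.1.5, which specifies no such contrast, and the registered outcome list says something different.

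**Dilution is conditional.** The plan nowhere says that the three surveys share one equally weighted 0/1 effect. A dose that accumulates would give 3-month rows partial exposure. This stands too. The dose option is only a possible safeguard, because the plan does not say which coding is primary, sets the form of dose after seeing the data, and counts components without regard to subject.

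**An early survey is ordinary.** A reader might infer that nothing relevant has been delivered by 3 months, so that a null there says nothing about the programme. The documents do not support that. Relationship, reproductive-health and mentoring content is due by then, Native Voices draws on a curriculum that covers condom use and negotiation, and the systems component runs reservation-wide (Section 2.3.5). Parts of H2, such as partners and onset of intercourse, could plausibly respond to early content. The case is limited to condom, birth-control and substance-with-sex outcomes.

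**Conclusion.** The concern holds in a limited form. Given numbered order and an even pace, the 3-month survey precedes NS 9-13 and NS 15, so for condom, birth-control and substance-with-sex outcomes it measures early, partial exposure. The record contradicts itself on whether 3 months is a primary time, and the model neither isolates 3 months nor yields the 12-month estimate.

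If 3-month rows are coded 1, the estimate falls from 0.14 to 0.093 with no early effect, or to 0.109 with one third of it, under equal weights. Power falls to about 46% or 59% on the same standard error, and by less if the 80% is anchored to 12 months alone. The stepped-wedge illustration gives stronger dilution. All of these figures rest on an assumed early effect, assumed weights and an assumed survey layout.

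A reader might go further and conclude that the primary result is diluted, or that 456 is too small for this reason. Neither follows: a 12-month-only contrast is unaffected, and the sample size is stated for that time. With separate coefficients for each survey time the dilution disappears. What remains is interpretive: a 3-month null says little about the completed programme, and a 3-month change cannot be credited to sessions not yet given.

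**What to change.** 1. Align the registered primary outcome with the H1 parenthesis, so that 12 months is the primary time in both.
2. In Section 3.1.5, choose one of two forms. Either give 3 months its own exposure-time coefficient and make the 12-month contrast primary, or define the 3-month survey as a transition period whose rows are left out of theta for condom, birth-control and substance-with-sex outcomes. State in advance whether X is 0/1 or dose in the primary analysis.
3. Label 3-month results for these outcomes as early, partial-exposure and descriptive. Three months can stay an outcome time for content already delivered, such as the first mentoring topics.

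The change is to wording only and needs no new data. Excluding the 3-month rows makes the standard error roughly 6% to 14% larger than in the pooled model, depending on the layout assumed. A contrast that uses the 12-month survey alone is less precise than the pooled one (a ratio of 1.225 in the simple variance model), but it is the contrast for which the plan states its sample size. The study also gives up any early-effect claim for these outcomes.
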